Research Protocol

THE EFFECT OF MODAFINIL ON CONGITION AND SUBJECTIVE WELLBEING IN HEALTHY ADULTS

Chief and Principal Investigator

[name], Professor of Clinical Neuropsychiatry, Cambridge School of Clinical Medicine & Behavioural and Clinical Neuroscience Institute University of Cambridge, Department of Psychiatry, Addenbrooke's Hospital [name] [contact] Email: [contact]

Research Team:

[name], Department of Experimental Psychology & BCNI, University of Cambridge (Head of Experimental Psychology, University of Cambridge)

[name], Department of Clinical Neurosciences & BCNI, Honorary Consultant neurologist at the Cambridge University Neurology Unit & MRC Cognition and Brain Sciences Unit

[name], Department of Psychiatry & BCNI, University of Cambridge,

Aims of the Project

This project aims to investigate the effect of modafinil on cognitive performance, divergent thinking and subjective well-being in healthy participants. The main task for this project is to address whether the same effects of acutely administered modafinil on cognitive function are observed across four testing sessions or whether its effects exhibit tolerance. Participants' divergent thinking, cognitive performance and subjective well-being will be investigated in a between-subjects parallel design study.

Two groups each of 32 healthy participants will attend four separate sessions at the Wellcome Trust Clinical Research Facility (WTCRF), during which they will be tested on objective measures of divergent thinking tasks, a computerised neuropsychological battery, and on well-validated questionnaires quantifying subjective well-being. Participants will be randomly allocated to one group and will consistently receive either a dose of modafinil (200mg) (Modafinil group) or a placebo (Control group) prior to testing on all four sessions.

All subjects will undertake CANTAB tests and different versions of the divergent thinking tasks. Based on the evidence that modafinil enhances executive planning and working memory in healthy adults (Turner et al 2003), we predict that healthy individuals in the Modafinil group will perform better in the divergent thinking tasks and in the cognitive performance tasks. Furthermore, we expect a specific subjective well-being effect to be associated with recurrent modafinil use in healthy young adults.

Background

Modafinil (Provigil, 1997) is a novel drug which has a demonstrable efficacy in the treatment of daytime sleepiness associated with narcolepsy (Benerjee et al., 2004). Studies with healthy volunteers,

including those conducted by our research group, showed that modafinil improves some aspects of neuropsychological task performance, possibly through improved inhibitory control (Turner et al., 2003; Baranski et al., 2004; Muller et al., 2004; Randall et al., 2005). For instance, Turner et al. (2003) assessed the cognitive enhancement potential of modafinil on sixty young healthy male volunteers who either received a single oral dose of placebo, or 100mg, or 200mg of modafinil before undertaking tasks on working memory and attention. Modafinil significantly improved performance of digit span, visual pattern recognition memory, spatial planning and stop signal reaction time. It also significantly improved performance on tests on decision making and delayed matching to sample.

Modafinil also had a significant beneficial effect on working memory and executive attention in patients with neuropsychiatric disorders including depression (Padala, Burke, & Bhatia, 2007), schizophrenia (Turner et al., 2004b), and Parkinson's disease (Happe, Pirker, Sauter, Klosch, & Zeitlhofer, 2001). Turner et al., (2004a) also found that modafinil enhanced cognitive functioning in ADHD patients, who after 2-3 hour post administration of modafinil, significantly improved on tests of short-term memory span, visual memory, spatial planning, and stop-signal motor inhibition. On several measures, modafinil increased sustained attention accuracy whilst slowing response latency.

However, most previous studies have significant shortcomings, as they only investigated the acute effect of modafinil on cognition and therefore are not able infer whether the same effects modafinil on cognitive function are consistently observed in subsequent testing sessions (Pubmed review 07/12/2009).

Our aims are (i) to further characterise possible cognitive enhancing effects of modafinil by using a broader range of test (including divergent thinking, or 'creativity') and a more difficult cognitive test battery to avoid possible ceiling effects on some tests and determine whether the beneficial effects of modafinil are in a restricted range of tests or functions as appears previously to have been the case. (ii) to test whether any drug effects exhibit behavioural tolerance, i.e. diminishing with repeated testing. These aims will be achieved with a double blind, placebo controlled study that measures participants' cognitive performance over four weekly sessions.

We will investigate the effect either of one weekly dose of modafinil (200mg) or placebo for four sessions on tests of divergent thinking, cognitive performance and subjective well-being in healthy adults. This will be accomplished by employing reliable divergent thinking tasks, a well-validated cognitive battery and a sensitive subjective well-being questionnaire.

Predictions with regard to the research questions/objectives:

1. For Cognitive and Divergent thinking

- We predict that participants treated with modafinil will perform significantly better in the above named cognitive tasks and divergent thinking compared with the placebo group.
- The effect of modafinil on divergent thinking is difficult to predict but it is expected that there will be an improvement at least in the first session.
- Modafinil is efficacious for sustaining and restoring objective performance and alertness in sleep deprived and non sleep deprived humans (Wesensten, 2006), it is therefore predicted that modafinil will have a significant effect (two-tailed) on ratings of subjective well-being in healthy adults.
- We expect that modafinil will have a greater significant positive effect on subjective well-being and divergent thinking in healthy participants with low scores at baseline compared to healthy participants with high scores at baseline.
- 2. First session compared with the following session

• Finally, it is predict that there will be a significant difference between the effect of modafinil on divergent thinking scores, cognitive performance and subjective well-being in the first testing session in comparison to the other three sessions.

Methods:

Study Design: This is a double-blind, placebo-controlled, between subjects, parallel design study. 2 x 30 participants will receive either a single oral dose of a lactose placebo or 200mg of modafinil for four occasions (one dose per week to allow for drug washout). Participants will either be identified via the Behavioural and Clinical Neuroscience Institute participant panel or via an advertisement. Once potential participants are interested in taking part in the study, they will be sent an information sheet and contacted within 24 hours. Participants will be informed of the details of the study and will have the opportunity to ask questions or withdraw from it at any time.

Exclusion criteria: Prior to the first testing session, possible participants will be screened through telephone and any participant with any significant psychiatric history, visual or motor impairment or the concurrent use of any psychotropic medications or any medication contra-indicated with modafinil will be excluded. In addition, participants with a history of hypertension, cardiac disorders, epilepsy or drug or alcohol abuse will also be excluded. The two groups will be matched for age, verbal abilities by using the National Adult Reading Test, (Nelson, 1991) and education level. All participants will be advised not to consume alcohol or caffeine-containing drinks for 12 hours before the study.

Testing procedure: On a convenient date, participants will be asked to attend the WTCRF at Addenbrooke's Hospital on four occasions, separated by a maximum of one week. Once participants arrive at the WTCRF at about 8:30am, we will confirm their details and ask them to complete a personality and NART measures. After that, we will measure their blood pressure. Then we will give participants some capsules to swallow with water. These capsules will contain either a drug (modafinil), or a placebo (an inert lactose pill) –neither the participant nor the researcher testing the participant will know which pill participants are given on a particular day. A physician ([name]) will be available to provide medical assessment if participants experience any adverse events related to participation.

After ingesting the pill, participants will then rest in a quiet area where they can read books or magazines, and watch television for one and a half hours. Similar to previous research, participants will be tested 2 hours post-drug administration, for approximately 2.5 hours. At 2h participants will complete a divergent thinking task, a computerized cognitive performance task, and two subjective well being questionnaires. During the computerized testing, we will measure their blood pressure again.

After the first session, participants will return to the research facility for three more times separated by a week. In the subsequent three sessions, participants will undertake further sessions which will be similar in procedure but using different versions of the tests where possible. A psychologist will instruct the volunteers on how to perform each task and will provide feedback if necessary.

Measures

Total Testing time (120 min)

Measures of the divergent thinking will be drawn from the following:

• Match Stick problem (Knoblich et al., 1999) which measures how healthy adults learn to override the imperatives of past experience in the face of novel conditions (12 min).

- Wallach and Kogan's (1965) test of divergent thinking task assessing pattern meaning, line drawings, similarities and alternative uses tasks (10 min).
- A short version of the original Hayling task (Burgess and Shallice, 1997) that measures cognitive flexibility (7 min).

Cognitive measures will be drawn from the well established CANTAB neuropsychological test battery: (Sahakian and Owen, 1992-www.camcog.com). All participants will receive the same tests in the same order. All computerised tasks will be run on an Advantech personal computer (Model PPC-120T-RT), and responses will be registered either via the touch-sensitive screen or a response key, depending on the task. The following cognitive test battery will consist of:

The Stop Signal Test (Logan, Cowan et al. 1984), a 20 minute task assessing the inhibition of motor responses to an auditory 'Stop' signal.

- Reward sensitivity (Cools et al. 2005), a 15 minute reaction time task assessing ability to respond to changing reward value.
- A version of 5-Choice Serial Reaction Task which is suitable for humans (Robbins, 2002) (5 min).
- Digit Span assessing working memory and vigilance.(5 min)
- The Paired Associates Learning (PAL) task which tests the ability to learn and form visuo-spatial associations (Sahakian et al., 1988) (10 min)
- Pattern Recognition Memory (PRM) which is a two choice test of abstract visual pattern recognition memory (Mehta et al., 1999) (5 min).
- The Delayed Matching to Sample (DMTS) which is a 4 choice of simultaneous and delayed matching to sample abstract pattern task with distractors (Robbin et al., 1994) (10 min).
- The Rapid Visual Information Processing (RVIP) task measuring sustained attention (7 min)
- The 'one-touch' Tower of London spatial planning task (NTOL) which measures planning (Owen et al., 1995) (10 min) difficult version

Short self-report questionnaires, consisting of

- SF-8: SF-8 to measure participants' subjective wellbeing (5 min).
- Creative Personality Scale (CPS) for the Adjective Checklist by Gough's (1979) measuring whether participants are high or low in creativity(7 min).
- Visual Analogue Scale (VAS) (Bond & Lader, 1974) which assesses participants mood before, during and after the tablet administration (2 min).

Sample Size and Analysis: The Sample 30 per group was estimated to provide sufficient statistical power based on previous within-subject medication studies (Turner, 2003;). For a large effect size of modafinil study (d=0.52), the statistical power software (GPower) indicates a power of 0.95 to detect a large effect size with 0.05 error (i.e type I false positive error 5%) with 30 participants. A stronger interaction between modafinil and group (modafinil vs placebo x group) with a large effect size d=0.52, for false positives (a=0.05) with 30 participants in each group yields a power of 0.95. An interim analysis will be performed after the completion of the first sixteen participants in each group

Statistical analysis: All data will be analysed using Windows versions of SPSS (Version 15). To investigate the effect of experimental treatment on test performance, differences between group mean (or median) performance for group scores will be analysed using a one-way and repeated analysis of variance (ANOVA) or the equivalent non-parametric Kruskal-Wallis ANOVA. To clarify the nature of any such differences, planned orthogonal contrasts comparing the effect of modafinil, and the effect of placebo with the drug group, will be performed where appropriate. In instances where

several readings are taken for the same score, repeated measures ANOVA will be used to test the effects of relevant independent within- and between-subjects variables. As our hypotheses are both one and two directional, all tests will employ two-tailed statistics threshold at p<0.05.

This is small scale study using modafinil as a pharmacological tool to neuromodulate cognitive performance and subjective wellbeing in healthy adults .It is therefore not a clinical trial under MHRA definitions.

Main Ethical Considerations:

Several areas have been considered here.

- 1. Confidentiality. We follow standard good research practices within our departments, to ensure confidentiality of electronic and hard copy data, in keeping with the Data Protection Act. Hard data are kept locked, and electronic data are anonymised and encrypted. We collaborate with other members of the University and require similar adherence to DPA and confidentiality by collaborators. We do not anticipate data sharing outside the UK. Data will be stored for maximum of 10 years within the department.
- 2. Safety. The safety of participants is paramount. This study involves a single standard dose (200mg) of modafinil, a medication with an excellent safety profile that is currently licensed for the treatment of daytime sleepiness. Modafinil has been used previously in multiple LREC-approved studies including male and female participants within the Department of Psychiatry (University of Cambridge) with no adverse reactions or problems reported. We have used modafinil with both patients (Backwell et al., 2008, CamREC reference number 04/076; Turner et al., 2004a, b) and Healthy adults (Winder-Rhodes et al., 2009-CamREC reference number 06/Q0106/47; Turner et al., 2003) and consistent with research evidence modafinil is safe (Deroche-Gamonet et al 2002; Billiard et al 1994) and current dose of modafinil has been well tolerated in studies run by members of our research team (e.g., Turner et al., 2009; Turner et al., 2004b). Furthermore, patients who are taking other forms of psychiatric or non-psychiatric medications contraindicated for use with modafinil will not be included in this study. The structured health interview as well as the information provided to participants will screen for pregnancy, breast-feeding, and volunteers who are attempting to become pregnant (see protocol and information sheet).

Participants will be screened via questionnaire to ensure they have no history of relevant medical problems (e.g. hypertension, heart disease), and are not taking other medications which might adversely interact with modafinil. A physician ([name]) will be available if participants experience any adverse events related to participation.

3. Consent. All participants will, by definition, have the capacity to provide informed consent. As this study investigates healthy young participants, vulnerable participants, including pregnant women, will not be included in this study. Consent procedures include enough information and enough time to make a decision to participate, and we stress the voluntary nature of participation and ability to withdraw. We have written our information sheets and consent sheets so as to be complete, but concise and

comprehensive for the lay participant. In addition, participants will have the ultimate decision to participate in this study.

4. Comfort. Furthermore, there is no reason to believe that the neuropsychological testing procedure should carry any adverse consequences for the health of participants. Each task takes under 20 minutes; all tasks are administered by a trained researcher with psychology experience to at least post-graduate level and clinical experience.

The cognitive testing battery requires participants to interact with a computer equipped with a touch-sensitive screen. Participants will perform the cognitive testing battery for approximately 2.5 hours. Short breaks will be included throughout the battery, and participants will be reminded that they can take a break at any time by asking the researcher. The procedures used in this experiment will neither be physically stressful nor impinge on the safety of the participants. The images and feedback that are presented are also not emotional and have not caused any distress in related studies of patients or healthy controls. Testing will stop if a participant reports excessive frustration or appears tired.

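### The low-versus-high baseline prediction, with only group-comparison methods named, implies a split of a graded score; if one is made, roughly a third of the information on that interaction is lost

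*Protocol*

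**What the plan says.** Three places in the Protocol bear on this.

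- *Predictions with regard to the research questions/objectives*, item 1, expects modafinil to help some participants more than others, on divergent thinking as well as well-being. The contrast it draws is "healthy participants with low scores at baseline compared to healthy participants with high scores at baseline". It gives no cut-point and names no test for this prediction.
- *Measures* lists the Creative Personality Scale as "measuring whether participants are high or low in creativity".
- *Statistical analysis* says that differences between group means or medians "will be analysed using a one-way and repeated analysis of variance (ANOVA) or the equivalent non-parametric Kruskal-Wallis ANOVA". It adds planned orthogonal contrasts and, where a score is read several times, that "repeated measures ANOVA will be used to test the effects of relevant independent within- and between-subjects variables". No regression, covariate or continuous moderator is named.

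Timing also matters. *Testing procedure* places a personality measure before the capsule, then says: "At 2h participants will complete a divergent thinking task, a computerized cognitive performance task, and two subjective well being questionnaires". In *Measures*, the visual analogue scale "assesses participants mood before, during and after the tablet administration".

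**The concern.** The prediction contrasts two kinds of participant, a graded scale is described as sorting people into two kinds, and the listed methods compare groups. One-way ANOVA and Kruskal-Wallis can take a baseline score only as a grouping factor. An analyst following this text would most naturally form a low group and a high group and test group by treatment.

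Splitting treats everyone on the same side of the cut as alike, so a real dependence of the modafinil effect on baseline is missed more often. With 30 per arm, a median split leaves about 30/2 = 15 participants in each treatment-by-level cell. If the cut were chosen with results in view, the finding would also depend on that choice. What is at stake is one of the stated hypotheses, though not the main one.

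**Working it through.** **The plan's own figure.** The Protocol gives no power or information figure for a baseline-by-treatment interaction, so there is none to reproduce. Its only power figure (*Sample Size and Analysis*: 0.95 for d = 0.52 with 30 per group) concerns the treatment effect and an interaction written as modafinil versus placebo by group. It is not used below as a claim about this moderator.

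**Inputs.** From the Protocol: 30 per arm (*Study Design*; the Aims give 32, which changes little here) and two-sided alpha 0.05. Assumed: one outcome score, normal baseline score x with SD 1, linear interaction, residual SD 1, cut at the median.

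**Information kept by a split.** For a normal score cut at proportion p, the relative efficiency for a linear interaction is φ(z_p)² / [p(1 − p)].

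- At the median: 2/π = 0.637, a loss of 1 − 0.637 = 36%. Sixty participants then count as 60 × 0.637 ≈ 38.
- Other cuts of a normal score: 40/60 loses 38%, 33/67 loses 41%, 25/75 loses 46%.
- Median cut of other shapes: uniform loses 25%; t with 5 df 46%; lognormal (log SD 0.5) 48%; exponential 52%.

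**Hand check.** Let δ be the difference in mean modafinil effect between the low and high halves. The halves' mean x values are 2√(2/π) = 1.596 SD apart, so the slope difference is b = δ/1.596. For δ = 0.52, b = 0.326.

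- Continuous score: SE(b) ≈ √(1/30 + 1/30) = 0.258, so b/SE = 1.26.
- Split score: SE ≈ √(4/15) = 0.516, so δ/SE = 0.52/0.516 = 1.01.
- Ratio of squares: (1.01/1.26)² ≈ 0.64, agreeing with 2/π.

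**Power by simulation.** There were 15,000 simulated trials per row. The model was y = 0.3x + 0.52g + b·g·x + e, where g is treatment and b has a negative sign so that low scorers gain more. The interaction was tested by a t test on 60 − 4 = 56 df.

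| δ (SD) | Continuous | Median split | Points lost |
|---|---|---|---|
| 0 (type I error) | 0.049 | 0.048 | – |
| 0.52 | 0.224 | 0.162 | 6 |
| 0.80 | 0.448 | 0.315 | 13 |
| 1.04 | 0.664 | 0.477 | 19 |
| 1.30 | 0.841 | 0.651 | 19 |

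A second simulation, set by interaction slope and with baseline slopes of 0 and 0.5, shows the same pattern. Power is 0.48 against 0.31–0.33 at a slope of 0.52 SD per SD, 0.77 against 0.55–0.59 at 0.75, and 0.95 against 0.78–0.81 at 1.0.

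**The case against.** The strongest reply is that the Protocol never says it will split anything. Saying that low scorers gain more than high scorers is ordinary wording for a negative treatment-by-baseline slope. The sentence naming ANOVA concerns the effect of treatment on performance, and repeated measures ANOVA with unspecified relevant variables does not exclude a covariate. The scale description is one line in a list of measures, and nothing ties it to this prediction. How a secondary prediction is modelled is commonly left to the SAP, which is not at hand.

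Much of this stands, and it rules out several stronger readings that a reader might infer:

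- *That the Protocol prescribes a median split.* It states no split, cut-point or cell size; the split is implied only by the three places read together.
- *That a third of the information is certain to be lost.* That figure needs a split, a normal score and a median cut.
- *That the absent cut-point is itself an error.* That detail may sit in the SAP.
- *That the Protocol claims 0.95 power for this interaction.* Its d = 0.52 is not tied to a baseline moderator; using 0.52 SD here is only an anchor. At that value power is poor either way, and the larger gains need differences of 0.8 SD or more.

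The objection also rightly notes that no divergent-thinking or well-being questionnaire score is described before dosing. A continuous term cannot repair that: a first-session score taken 2 hours after the capsule could already be affected by treatment, whether split or not.

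What the objection does not remove is the wording. If a continuous test is intended, the text misdescribes it; if a split is intended, it wastes data. The same rewording settles both.

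**Conclusion.** The point holds in conditional form. The Protocol's wording and its list of methods imply that a graded baseline score will be made into two groups. If that is done at the median of a normal score, the loss is 36% of the information on a linear interaction, and about 25% to 52% across the other distributions and cuts examined. With 30 per arm, that costs about 6 power points at an assumed difference of 0.52 SD between halves and about 19 at 1.04 to 1.3 SD, with type I error near 5% either way.

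These figures rest on one outcome score, a linear interaction and residual SD 1; they are not the Protocol's. The point is worth correcting because the better method is nearly free. It does not affect the main treatment comparison.

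**What to change.** - In *Predictions*, reword the item so that the modafinil effect is expected to decrease as the baseline score increases, and name the score that counts as baseline.
- In *Statistical analysis*, test it with a treatment by baseline-score interaction, the score entered as a continuous, centred covariate in the linear or repeated measures model. Report the slope difference with its 95% CI.
- Use only scores taken before dosing: the personality measure in *Testing procedure*, taken here to be the Creative Personality Scale because it is the only personality measure listed, and the pre-tablet visual analogue rating. For the latter, the first-session rating is the one that precedes every dose.
- In *Measures*, say that the Creative Personality Scale measures degree of creativity. Keep any low/high display descriptive, for example the fitted modafinil effect at the 25th and 75th percentiles.

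The cost is a few words and one model term; no new data or participants are needed. Approximate linearity is assumed and can be checked by plotting. One limit should be stated openly: these pre-dose scores measure trait creativity and mood, so the reworded prediction would concern those, not pre-dose divergent thinking or questionnaire well-being, for which no measurement is described.

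### Allocation is called both random and matched on age, NART and education, nothing reconciles the two, and the named analysis includes none of these variables

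*Protocol*

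**What the plan says.** **Allocation.** Aims of the Project in the Protocol states: "Participants will be randomly allocated to one group". Exclusion criteria, under Methods, states: "The two groups will be matched for age, verbal abilities by using the National Adult Reading Test", and adds education level as a third matching variable. No list, strata, minimisation or pairing is described.

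**Timing.** Under Testing procedure, staff will "ask them to complete a personality and NART measures" on arrival. Blood pressure and then the capsules follow. The telephone screen described under Exclusion criteria covers medical and psychiatric history and medication, not the NART.

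**Analysis.** Under Statistical analysis, "differences between group mean (or median) performance for group scores will be analysed using a one-way and repeated analysis of variance", with Kruskal-Wallis as the non-parametric alternative. Where a score is read several times, "repeated measures ANOVA will be used to test the effects of relevant independent within- and between-subjects variables"; these variables are not listed. On the threshold, "all tests will employ two-tailed statistics threshold at p<0.05".

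**Mood.** Under Measures, the visual analogue scale (VAS) "assesses participants mood before, during and after the tablet administration".

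**The concern.** The two allocation statements describe different things. Random allocation balances age, NART and education only on average. Matched groups need a mechanism, and which one is used affects both concealment and the analysis. Allocation has to be settled before the first participant is dosed, so it belongs in the Protocol.

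The analysis text does not reflect the stated design either. One-way ANOVA and Kruskal-Wallis have one grouping factor and no covariate. Any outcome variance explained by age, NART or education then stays in the error term, although the trial means to record all three. The pre-dose VAS does enter the repeated-measures ANOVA, but as one more time level, which uses it less efficiently than a covariate would.

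At stake are clarity about how participants reach their arm, and precision in a small trial.

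**Working it through.** **Inputs from the Protocol.** 30 per group, d=0.52 and stated power 0.95 (Sample Size and Analysis); two-sided 0.05 (Statistical analysis). Aims of the Project gives 32 per group instead.

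**Assumed inputs.** The Protocol gives no R² for age, NART and education together, and no pre/post correlation for the VAS. R² is taken as 0.05 to 0.30, and r as 0.5 with 0.7 as a second case.

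**1. The Protocol's own figure.** For a two-sample t test the noncentrality is d·√(n/2) = 0.52 × √15 = 2.01 on 58 df. Power is 0.51, or 0.53 with 32 per group. The stated 0.95 is not reproduced; by the normal approximation, d=0.52 would need 97 per group.

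**2. Adjusting for age, NART and education.** The residual SD becomes √(1−R²), so the effective effect is 0.52/√(1−R²). Three df are spent.

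| R² (assumed) | Effective d | Power |
|---|---|---|
| 0 | 0.520 | 0.51 |
| 0.05 | 0.534 | 0.53 |
| 0.10 | 0.548 | 0.55 |
| 0.20 | 0.581 | 0.60 |
| 0.30 | 0.622 | 0.66 |

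Spending 3 or 4 df costs about 0.001 in power. Reaching 0.95 would need an R² of about 0.70.

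**3. If balance is forced and then left out of the model.** In the limit of perfect balance, the true type I error of the nominal 0.05 test is 2(1−Φ(1.96/√(1−R²))). This is 0.028 at R²=0.2 and 0.019 at R²=0.3. Simulation with 40,000 runs gives 0.039 at R²=0.1 and 0.020 at R²=0.3. The error lies below 0.05 throughout.

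**4. If allocation is simple randomisation.** The SE of a group difference in any covariate is √(2/30) = 0.26 SD, so chance gaps of up to about 1.96 × 0.26 = 0.5 SD are ordinary. The unadjusted standard error already allows for this, and the test keeps its 0.05 level.

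**5. Mood, one pre/post pair.** A change analysis has effective effect d/√(2(1−r)); using the pre-dose score as covariate gives d/√(1−r²).
- r=0.5: 0.52/1 = 0.52, power 0.51; 0.52/√0.75 = 0.60, power 0.63.
- r=0.7: 0.52/√0.6 = 0.67, power 0.725; 0.52/√0.51 = 0.73, power 0.792.

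**6. The tolerance question.** The contrast of session one with the later three is taken within person. Age, NART and education are fixed over four weekly sessions, so a constant contribution βx cancels in the difference. Adding them as main effects gains essentially nothing there.

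**The case against.** The strongest objection is that covariates are commonly left to a statistical analysis plan, which may exist but is not shown. The Protocol names families of tests, excludes no covariate, and leaves some room through its reference to relevant between-subjects variables. This stands to the extent that the text does not prove that no adjustment will be made. It does not remove the point: the room applies only to repeated readings, and the Protocol sets out a matched design while naming models that omit the matching variables.

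Matching may also mean only a group-level comparability check, or minimisation, either of which is compatible with random allocation. That is possible, but the text says neither.

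Four stronger readings are tempting and are not supported:
- **The unadjusted test is invalid or inflates false positives.** It is valid under simple randomisation and conservative under forced balance. The type I figures of 0.028 and 0.019 need perfect balance, which nothing in the Protocol promises.
- **Staff will steer allocation on the spot once the NART is scored.** The timing leaves the question open, but no such step is described.
- **The pre-dose VAS is ignored.** It enters the repeated-measures ANOVA as a time level. Preferring it as a covariate is a matter of efficiency. The power comparison above also reduces the before, during and after readings to one pair.
- **Adjustment repairs the power claim.** It does not, within any R² considered here.

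It is also fair that a single R² for all tasks has no support in the Protocol, and that at 0.05 the gain is only about 2 points of power.

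**Conclusion.** The point holds in a limited form. The firm part is textual: random allocation and matching are both stated, nothing connects them, and the named analysis contains none of the matching variables.

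The statistical part is a loss of precision. At d=0.52 and 30 per group, adjustment would raise between-group power from 0.51 by about 2 to 15 points (to 0.53–0.66) for an assumed R² of 0.05 to 0.30. For mood, the pre-dose covariate gives 0.63 against 0.51, assuming one pre/post pair and r=0.5. These gains apply to between-group comparisons only, not to the group-by-session contrast, which the Aims present as the main task. The failure of the stated 0.95 on its own inputs is a larger and separate problem. The change is worth making because it is cheap, not because the planned test would mislead.

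**What to change.** 1. Replace the matching sentence with a statement of method: either a concealed random list, or stratification or minimisation with a random element on age, NART and education level. If NART is a balancing factor, say when it is scored and how allocation stays concealed from the researcher who tests the participant. If it is not, say that the groups will only be described on these variables.
2. Name age, NART score and education level as prespecified covariates in the between-group comparisons of cognitive, divergent-thinking and well-being scores. Say what replaces Kruskal-Wallis where covariates are needed, since that test cannot carry them.
3. For post-dose mood only, use that session's pre-dose VAS as a covariate.
4. Do not present the adjustment as a gain for the tolerance contrast or as support for the 0.95 power.

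The cost is a few sentences, a few model terms and 3 to 4 of 58 degrees of freedom, depending on how education level is coded. NART and pre-dose VAS are already scheduled, and age and education level are needed for the matching as stated.
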